3.5 Safety variables

3.5.1 Adverse events

AEs: The number and percentage of patients who experienced 1 or more treatment-emergent adverse event (TEAE), and the number of TEAE occurrences will be tabulated by treatment group. An AE is considered TEAE if the event occurs after first dose of IMP up to 42 days after the administration of the last dose of IMP or was present prior to the date of the first dose of IP, but increased in intensity after IP administration. All events present before first IMP are considered non-TEAEs.

Adverse events occurring before administration of IP (ie, not treatment-emergent) and the number of occurrences will be reported in the same way as TEAEs in a different Table.

A TEAE that occurs during a wash-out period will be associated to the last treatment taken. An AE that occurs more than 42 days after the last IP administration will not be counted as a TEAE.

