8.3.4 Adverse event data collection

The following variables will be collect for each AE:

- AE (verbatim).
- The date and time when the AE started and stopped.
- Maximum intensity.
- Whether the AE is serious or not.
- Investigator causality rating against the IP(s) (yes or no).
- Action taken with regard to IP(s).
- AE caused patient's withdrawal from study (yes or no).
- Outcome.

In addition, the following variables will be collected for SAEs:

- Date AE met criteria for serious AE.
- Date Investigator became aware of serious AE.
- AE is serious due to.
- Date of hospitalisation.
- Date of discharge.
- Probable cause of death.
- Date of death.
- Autopsy performed.
- Causality assessment in relation to study procedure(s).
- Causality assessment to other medications.

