9.4.2 Safety analyses

All demographic and baseline characteristics, safety outcomes and other variables will be analysed using the safety population.

Safety will be assessed by descriptive analysis of AEs, vital signs, ECGs and clinical laboratory assessments.

All analyses of safety and tolerability outcomes will be performed on the safety population. Individual safety and tolerability data will be provided in data listings and summarised as appropriate by treatment. Continuous variables (laboratory parameters [including i-STAT], vital signs and ECG) will be summarised using descriptive statistics (n, mean, SD, minimum, median, and maximum) as appropriate by scheduled assessment time point. Where applicable, data will be summarised for the observed value, and for the corresponding change from baseline/screening. Categorical variables will be summarised in frequency tables (counts and percentage). Change from baseline will be calculated as the differences between the post-dose value at each time point and the morning value prior to administration of the IP.

For all variables, 12-lead ECG parameters, vital signs and laboratory tests (including i-STAT), baseline values will be defined as the values obtained prior to the morning IP administration on Day 1 of Visit 3.

Any clinically relevant new physical examination findings or worsening of a pre-existing physical examination finding that were to be recorded as an AE will be presented with the AEs.

AEs: The number and percentage of patients who experienced 1 or more treatment-emergent AEs (TEAEs), and the number of TEAE occurrences will be tabulated by treatment group. Adverse events occurring before administration of IP (ie, not treatment-emergent) and the number of occurrences will be reported in the same way as TEAEs. An AE will be considered a TEAE if it was not present prior to the date of the first dose of IP or was present prior to the date of the first dose of IP, but increased in severity after IP administration. A TEAE that

occurs during a wash-out period will be associated to the last treatment taken. An AE that occurs more than 42 days after the last IP administration will not be counted as a TEAE. TEAE tables will be tabulated by system organ class, preferred term, intensity, causality, action taken, outcome, seriousness criteria and treatment group using descriptive statistics.

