4.4.1.1 Adverse events

All reported AEs will be listed along with the date of onset, date of resolution (if AE is resolved), investigator's assessment of intensity, outcome, action taken with IMP, and possible relationship to study drug.

Any AE occurring before the first dose of IP, or more than 42 days after the last dose of IP, will be considered as non-TEAE, it will be included in the data listings but will not be included in the summary tables of AEs.

Multiple occurrences of a TEAE in the same patient will only be counted once overall considering start date as the first day of first occurrence and stop date the last day of the last occurrence and the TEAE will assigned to the treatment of the first occurrence period study drug. Multiple occurrences of a TEAE in the same patient for the same treatment will only be counted once for that treatment.

The number of patients/event will be tabulated also by preferred term, and treatment.

In the case that, within a treatment period, a patient has more than one episode of the same preferred term with different levels of intensity, action taken, outcome causality or seriousness, then the maximum intensity level, action taken (i.e. withdrawn) and outcome (i.e. fatal), causality level (i.e. related), or seriousness level (i.e. serious), respectively will be used. The following ordering will be used to define maximum intensity level, action taken, outcome causality level, or seriousness level :

- Intensity: Mild < Moderate < Severe
- Causality: No < Yes
- Seriousness: No < Yes

- Action taken: Unknown < Not applicable < Dose not changed < Drug interrupted < Drug withdrawn
- Outcome: Unknown < Recovered/resolved < Recovered/resolved with sequelae < Recovering/resolving < Not recovered/not resolved < Fatal

A general summary of all TEAEs will show the number and percentage of patients with

- Any TEAE
- Any TEAE with outcome = death
- Any TESAE (including events with outcome = death)
- Any TEAE leading to discontinuation of IP
- Any TEAE leading to withdrawal from study

The total number of TEAEs will be presented for the following categories;

- All TEAE
- All TEAE with outcome = death
- All TESAE (including events with outcome = death)
- All TEAE leading to discontinuation of IP
- All TEAE leading to withdrawal from study

The number and percentage of patients who experience one or more TEAEs will be tabulated by treatment and by:

- SOC and PT .
- PT, and maximum reported intensity

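### SAP 3.5.1 both counts and excludes pre-dose adverse events that worsen on treatment, and no rule assigns worsening to a later crossover period

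*SAP*

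**What the plan says.** Protocol 9.4.2 treats an event as treatment-emergent if it was absent before the first dose of IP, or if it "was present prior to the date of the first dose of IP, but increased in severity after IP administration". It contains no sentence that takes this second limb back.

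SAP 3.5.1 keeps both limbs. The second covers an event that "was present prior to the date of the first dose of IP, but increased in intensity after IP administration". The sentence directly after it reads "All events present before first IMP are considered non-TEAEs". SAP 4.4.1.1 adds: "Any AE occurring before the first dose of IP, or more than 42 days after the last dose of IP, will be considered as non-TEAE", and keeps those events out of the AE summary tables. SAP 3.5.2 applies the same date rule to SAEs. SAP section 6, which lists departures from the protocol, does not mention the TEAE definition.

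On attribution, SAP 3.5.1 gives a wash-out event to the preceding treatment. SAP 4.4.1.1 assigns repeated occurrences, in the overall count, to the treatment of the first one, and also counts a TEAE once per treatment.

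On data, protocol 8.3.4 collects for each AE a start, a stop and "Maximum intensity". It lists no intensity at onset or at dosing, and no date on which intensity changed. The same list does ask for the date on which an event became serious.

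**The concern.** A programmer building the TEAE flag finds one clause that includes worsened pre-dose events and a following sentence that excludes them. Sections 3.5.2 and 4.4.1.1 offer no exception that would settle it. Two competent programmers could produce different main tolerability tables from the same data.

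Safety and tolerability is a stated objective, and this design makes pre-existing events plausible. AEs are collected from consent. All patients take ipratropium during run-in and wash-out, and salbutamol is available as rescue throughout. Protocol 2.3 names dry mouth as the most frequent side effect of inhaled LAMAs, and palpitations, headache and tremor for beta-agonists. An event of the same classes as AZD8871 may therefore already be on record when a period starts, and its worsening would be one form of tolerability signal.

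**Working it through.** The plan gives no figure on this point, so the check compares the texts and then traces cases through them.

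**Texts side by side: an event present before the first dose that worsens after it**

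| Source | Classification |
|---|---|
| Protocol 9.4.2 | TEAE |
| SAP 3.5.1, worsening clause | TEAE |
| SAP 3.5.1, next sentence | not a TEAE |
| SAP 4.4.1.1 (AEs) | not a TEAE if dated by onset; no exception for worsening |
| SAP 3.5.2 (SAEs) | same as 4.4.1.1 |
| SAP section 6 | no change declared |

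The second and third rows cannot both be programmed. If the third prevails, the worsening clause has no content. SAP 3.5.1 sends pre-dose events to a separate table of the same layout, while 4.4.1.1 sends them to listings only, so that also needs reconciling.

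**Which first dose?** The worsening clause does not name a period. SAP 3.1.1.2, when imputing missing AE start dates, ties treatment-emergence to the first dose in the study. SAP 3.1.2 says so explicitly when it means each period. The natural reading of 3.5.1 is therefore study-wide.

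**Cases**

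1. *Onset in run-in, worse in Period 1, one continuing record.* The texts conflict as in the table. One maximum intensity between one start and one stop also does not show whether the rise came before or after dosing, so the worsening clause cannot be applied from the fields in protocol 8.3.4.
2. *Same event, worsening entered as a new AE dated after dosing.* The new record begins after first dose and is a TEAE under the first limb. The contradictory sentence then does little harm.
3. *Onset in Period 1 or its wash-out, worse in Period 2, one continuing record.* The event is already a TEAE. The wash-out rule covers onset, and the overall-count rule covers repeated occurrences. Neither says which treatment owns a worsening, and the record does not show the period in which it happened.
4. *Same event, worsening entered as a new record.* The once-per-treatment count can place it under the Period 2 treatment, but the overall count still goes to the first occurrence.

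**How many patients could be exposed by design** (protocol 6.3, Table 4; 12 patients per sequence)

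- AZD8871 in Period 1: sequences A and B, 2 × 12 = 24.
- AZD8871 in Period 2: C and E, 2 × 12 = 24. In Period 3: D and F, 2 × 12 = 24.
- AZD8871 after an earlier period and wash-out: 24 + 24 = 48 of 72.
- The same count holds for the comparator and for placebo, because the six sequences are balanced.
- All 72 could carry an event over from run-in.

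**Possible size, by assumption only.** Suppose 10% to 30% of 72 patients have an AE ongoing on a period's Day 1, and 5% to 20% of those worsen:

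- low: 72 × 0.10 × 0.05 = 0.36 patients per period;
- high: 72 × 0.30 × 0.20 = 4.32 patients per period.

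Neither rate comes from the documents. With 54 (planned completers) to 72 (planned randomised) patients in a treatment column, one patient moves a percentage by 1/72 = 1.4 to 1/54 = 1.9 points.

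**The case against.** The best defence is that worsening may well be captured as its own AE. Appendix B 1 lets the term cover deterioration of something already present. Protocol 8.2.4 requires clinically relevant worsening on an ECG to be recorded as an AE, and 8.3.7 does the same for aggravated examination findings unless plainly due to COPD. SAP 4.4.1.1 foresees several episodes of one preferred term at different intensities within a period. The eCRF and its guideline are not in the documents. A reader might infer from 8.3.4 that the data cannot show worsening at all; that is established only for a single continuing record. What remains is that neither document requires a new record when a symptom such as dry mouth worsens, so sites may differ.

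A reader might also infer that worsened events vanish, or that an event worsening on AZD8871 is charged to placebo. Neither is supported. The events stay in a separate table or in listings. The contradictory sentence concerns events before any IMP, and no text assigns a later worsening to placebo. On that the plan is silent, which is a separate gap.

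Other mitigating points are fair. Ipratropium is withheld for at least 8 hours before Visits 3, 6 and 9 and through the treatment periods. Heart rate has its own mixed models and criteria relative to baseline, and laboratory tables have a category for worsening. AE analysis is descriptive in an exploratory study, and the rule applies to all three treatments, so no direction of bias is shown. These limit the consequences but do not resolve the conflict in wording.

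**Conclusion.** The contradiction inside SAP 3.5.1, and between it and protocol 9.4.2, is certain from the text. Sections 3.5.2 and 4.4.1.1 reinforce the exclusion, and section 6 does not declare it. Two related gaps also stand: no per-period worsening rule in a crossover, and no way to date worsening within one continuing record.

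The number of misclassified patients cannot be computed. The illustrative range of about 0 to 4 per period rests wholly on assumed rates. Efficacy is unaffected. This should be corrected because the main tolerability tables lack a single definition and the correction is cheap.

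**What to change.** 1. In SAP 3.5.1, delete the contradictory sentence or qualify it with *unless they increase in intensity after IP*. Carry the same exception into 3.5.2 and 4.4.1.1, and settle whether pre-dose AEs are tabulated separately or only listed.
2. Define worsening relative to the first dose of each period, and assign the worsened event to that period's treatment. State that the first-occurrence rule in 4.4.1.1 does not override this.
3. In the eCRF completion guideline, state that an AE that worsens after a period's first dose is entered as a new record, linked to the old one, with its own onset date and intensity.

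The SAP changes are a few sentences. The third item adds a small site instruction and a few more AE records, with no new assessment. Step 1 alone would not be enough: without step 3, the restored clause still could not be applied to a single continuing record.

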Study treatment administration compliance will be recorded in the e-Diary of the patient when the patient is not at the site. No dose modification is planned for this study.

Wash-out periods: Between each treatment period, there will be a wash-out period of 42 to 49 days. During this period, all patients will receive ipratropium 20 µg × 2 puffs 4 times per day (must be discontinued 8 hours before any pulmonary function test). A paper diary will be used to collect AEs and concomitant medication during run-in and wash-out periods.

Follow-up Visit: Patients will come to the site for a Follow-up Visit, 42 days (up to 49 days) after the last IP administration, for AE assessment, safety laboratory, ECG, vital signs and physical examination.

Statistical methods:

The analysis of all the efficacy variables will be performed on the Full Analysis Set (FAS) population. In addition, the primary efficacy variable will be also analysed using the Per-Protocol population.

All demographic and baseline characteristics, safety outcomes and other variables will be analysed using the safety population.

Pharmacokinetic parameters will be analysed in the PK population on the subset of 36 patients who will have specifically consented to participation in the PK assessments.

Analysis of the primary efficacy variable: The primary efficacy variable is the change from baseline in Trough FEV₁ at Day 15 (ie, after 14 days of treatment).

Baseline for FEV₁ will be defined as the mean of the 2 measured values for the corresponding variable (2 measurements 45 min apart, at -1 hour and -15 min), prior to the morning IP administration on Day 1 of each treatment period. If both are missing, the Visit 2 pre-bronchodilator value will be used instead.

Trough is defined as the mean of the FEV₁ values obtained at 23 hours and 23 hours and 45 min after the morning IP administration on Day 1 and Day 14 (ie, obtained on Day 2 and Day 15). On Day 8, Trough is defined as the mean of the FEV₁ pre-dose values (-1 hour and -15 min). If one of the values is missing, the available value will be used as Trough.

This variable will be analysed by means of a mixed model with fixed effects for treatment, sequence, and period. The patient will be fitted as a random effect and the pre-dose FEV₁ of each period will be included as a covariate.

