2.3 Benefit/risk assessment

Currently, no single molecule with dual β_2 -agonist and muscarinic antagonist properties is licensed for medical use, though similar molecules are currently in development (Wielders et al, 2013; Bateman et al, 2013). However, there is extensive and increasing experience from clinical practice regarding products with effect on each of these receptors separately and in free and fixed combination. The most commonly cited AEs of β_2 -agonists are palpitations, headache and tremor. At higher doses, tachycardia, hyperglycaemia, hypokalaemia and an increased corrected QT interval (QTc) may be seen. These effects can be monitored in clinical studies using standard safety monitoring. Examples of systemically mediated AEs caused by muscarinic antagonists are: dryness of mouth, dilated pupils, glaucoma, increased heart rate, urinary retention and constipation. However, systemic availability after inhalation is limited and the most frequently reported side effect after inhalation of the LAMAs is dryness of mouth, with irritation in the upper airways and cough reported as potential local side effects.

Findings in non-clinical toxicology and safety pharmacology studies with AZD8871 reflect the dual antimuscarinic and β_2 -adrenoreceptor agonist activities associated with the primary pharmacology of this compound and are summarised in the IB. PR prolongation and atrio-ventricular blocks were recorded in the dog single dose cardiovascular safety study at 0.36 mg/kg, a dose above those causing tachycardia. This dose was associated with a systemic peak plasma concentration of 5.14 ng/mL (4 times higher than the values observed at the highest dose tested in Part 1 of the study D6640C00001 in asthma patients). These changes can be monitored and a higher dose was not associated with any unexpected cardiac toxicity with AZD8871 in Part 1 of study D6640C00001 and during the 12 consecutive days of treatment with the first dose in study D6640C00003.

Study D6640C00001 was a 2-part, randomised, placebo-controlled, safety, tolerability, pharmacokinetic and pharmacodynamic study of AZD8871 delivered by inhalation in asthmatic and COPD patients. In Part 1, single doses of AZD8871 from 50 up to 2100 μ g were administered to asthma patients. Efficacy of the compound was apparent with Peak and

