5.3.4 Medication and other restrictions

1. Salbutamol should be withheld at least 6 hours before each visit where spirometry is performed up to the last spirometry procedure on that visit. However, patients are permitted to use salbutamol if its use is absolutely necessary during the visit, and with the approval of the Investigator.
2. Ipratropium should be withheld at least 8 hours before Visits 3, 6 and 9 and during all treatment periods. This medication is to be used during the run-in and wash-out periods.
3. Patients must abstain from any of the following:
 - Blood or plasma donation from Screening (Visit 1) until 3 months after the Follow-up Visit at the end of the study.
 - Scheduled in-patient surgery or hospitalisation during the course of the study (patients are not required to abstain from emergency treatment).
 - Restrictions on medications (prescribed or over-the-counter products) are defined in Section 6.5.

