Only patients who fulfil FEV₁ predicted values (FEV₁ ≥40% and <80% from predicted normal value and FEV₁/forced vital capacity (FVC) ratio <70%) postsalbutamol at Visit 2, will be started on the run-in period to assess clinical stability.

If the FEV₁ predicted values is not met, pulmonary function tests may be repeated at the latest, up to Day-14.

The duration of run-in period will be between a minimum of 14 and a maximum of 28 days (from Visit 2 to Visit 3). During the run-in period, all patients will receive ipratropium 20 µg x 2 puffs 4 times per day (must be discontinued 8 hours before any pulmonary function test). A paper diary will be used to collect AEs and concomitant medications during run-in and wash-out periods.

Treatment periods: After the screening period, patients must fulfil all inclusion criteria and no exclusion criteria prior to being randomised at Visit 3. Eligibility results will be used from the Screening period for any assessments that cannot be completed within Visit 3 (eg, laboratory assessments).

The duration of each treatment period will be 14 days. During the treatment periods, patients will receive all 3 possible treatments, with every patient receiving placebo in one of the periods in addition to their ICS mono-component therapy, if any. In each period, patients will receive two devices to ensure the double blindness of the study. Patients will receive one of the 3 following possible treatments in any given period, in a randomised manner:

- AZD8871 600 µg once daily
- Anoro[®] Ellipta[®] (55µg UMEC/ 22 µg VI) once daily
- Placebo once daily

[figure not shown]
Each of the 3 treatment periods will last for 14 days and will include 2 overnight stays at the study site and one ambulatory visit at the study site.

Each 14-day treatment period (except the last one) will be followed by a wash-out period of 42 to 49 days, during which patients will receive ipratropium 20 µg x 2 puffs 4 times per day (must be discontinued 8 hours before any pulmonary function test), in addition to their usual ICS therapy, if any.

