3.2.3 Prior and concomitant medications

All medications will be classified into anatomical therapeutic chemical (ATC) drug classes using the latest version of the World Health Organization (WHO DD+HD March 2017 or later) Drug Dictionary.

Any medications taken by the patient between 15 days prior to signing the ICF and prior to the first dose date of IP will be considered prior medication. The medications taken by the patient more than 15 days before signing the ICF will be not considered prior medication but will be listed in the general listing of all medications for the patient.

Any medication taken by the patient at any time between the date of the first dose (including the date of the first dose) of IP up to 24h after the last IP administration of each treatment period will be considered concomitant medication.

A medication is considered concomitant for a treatment if the start date of the medication is on or after the date of first dose in that treatment period and prior to or at 24h post last IP intake of the treatment period, or the start date is prior to the date of first dose in that treatment period and a stop date on or after the date of first dose in that treatment period (the medication is ongoing). If a medication is taken over multiple periods of treatment, it will be considered concomitant for all treatments taken in the different periods.

A medication is considered to be taken during wash-out periods if it is taken after 24h of IP intake on Day 14 and before the following treatment period.

Medications that start after one day post the date of last dose of IP during the overall study will not be considered concomitant.

For the purpose of inclusion in prior or concomitant medication summaries, incomplete medication start and stop dates will be imputed as detailed in Section 3.1.1.1.

Medications that start during the follow-up period (ie, that start after one day post the date of the last dose of IP during the study) will only be displayed in listings.

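### The TEAE tables pool 14 dosing days with about 42 off-drug days per treatment, and no table is limited to onset during dosing

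*SAP*

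**What the plan says.** SAP 3.5.1 treats an event as treatment-emergent if it occurs "after first dose of IMP up to 42 days after the administration of the last dose of IMP", or if it was present earlier and worsened. It adds: "A TEAE that occurs during a wash-out period will be associated to the last treatment taken". Protocol 9.4.2 has the same allocation rule and the same 42-day limit.

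On timing, SAP 1.2 says "The duration of each treatment period will be 14 days" and "Each 14-day treatment period (except the last one) will be followed by a wash-out period of 42 to 49 days". The Protocol Synopsis agrees: "Between each treatment period, there will be a wash-out period of 42 to 49 days". Of ipratropium, Protocol 5.3.4 says "This medication is to be used during the run-in and wash-out periods"; it is withheld during treatment periods.

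SAP 4.4.1.1 plans an overall TEAE summary and tables by treatment: by SOC and PT, by PT with maximum intensity, by PT with investigator causality, for fatal outcome, and for common non-serious events. All use the window above. Onset dates appear only in a listing.

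For medications the SAP does separate dosing from wash-out. Under SAP 3.2.3, a medication taken from first dose "up to 24h after the last IP administration of each treatment period will be considered concomitant medication", and one taken later belongs to the wash-out.

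**The concern.** Most of each treatment's TEAE window is time without study drug. In the wash-outs between periods, including the one after placebo, patients take ipratropium, a muscarinic antagonist. Its class effects overlap those expected of both active treatments. Protocol 2.3 says: "Examples of systemically mediated AEs caused by muscarinic antagonists are: dryness of mouth". A dry-mouth report in week 5 after the placebo period is counted under placebo exactly as one on Day 3 would be.

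This bears on questions the trial sets itself. Protocol 4.2 justifies the placebo arm partly by the wish to characterise safety better, and Protocol 2.2 aims for tolerability at least as good as that of LAMA/LABA combinations, to be judged by direct comparison. Background added to every treatment makes the treatments look more alike in relative terms, so it favours an impression of equivalence.

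**Working it through.** **The documents' own figure.** No power or precision is stated for adverse events. The timing inputs can be checked against the stated study duration per patient:

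- Minimum: 14 (run-in) + 3 × 14 + 2 × 42 + 42 = 182 days.
- Maximum: 28 + 3 × 14 + 2 × 49 + 49 = 217 days.

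Both match the stated 182 and 217 days.

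**Share of the window off drug.** 42 / (14 + 42) = 42/56 = 75%. If the 42-day limit runs from the last dose of the whole study, a 49-day wash-out after Period 1 or 2 counts in full: 49/63 = 78%.

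**Relative dilution.** Assume a constant background event rate, an on-drug rate ratio r, and an excess that persists f days after the last dose. Then

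pooled ratio = [(14 + f) × r + (42 − f)] / 56.

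For r = 2:

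| Excess persists after last dose | Calculation | Pooled ratio |
|---|---|---|
| 0 days | (28 + 42)/56 | 1.25 |
| 14 days | (56 + 28)/56 | 1.50 |
| 21 days | (70 + 21)/56 | 1.625 |
| 42 days | 112/56 | 2.0 |

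With f = 0, r = 1.5 reads as (21 + 42)/56 = 1.125 and r = 3 as (42 + 42)/56 = 1.50. With a 49-day wash-out counted in full, r = 2 reads as (28 + 49)/63 = 1.22.

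**Absolute excess and noise.** Let b be the background rate per day and f = 0. The expected excess in events per patient is 14b(r − 1) in either window. Treating counts as Poisson and ignoring within-patient pairing, the variance of the difference is 14b(r + 1) during dosing and 14b(r + 1) + 2 × 42b = 14b(r + 7) pooled. The pooled z-score relative to the on-treatment z-score is therefore √[(r + 1)/(r + 7)]:

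- r = 2: √(3/9) = 58%.
- r = 3: √(4/10) = 63%.

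**Percentage of patients affected.** The tables also report patients with an event, and that difference does shrink, because background events use up patients who could otherwise show an excess. Assume a 14-day placebo incidence of 10% (not in the documents), r = 2 and f = 0:

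- Dosing only: 10% against 1 − 0.9² = 19.0%; difference 9.0 points, ratio 1.90.
- Pooled: 1 − 0.9⁴ = 34.4% against 1 − 0.9⁵ = 41.0%; difference 6.6 points, ratio 1.19.

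Over assumed placebo incidences of 2% to 20%, the on-treatment ratio runs from 1.98 to 1.80 and the pooled ratio from 1.24 to 1.14.

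**The case against.** The strongest defence is pharmacological. Protocol 4.2 bases the wash-out length on the terminal half-lives of AZD8871 and its metabolite, and SAP 4.3.1.1 allows for measurable pre-dose concentrations on Day 1. A 42-day window is therefore a coherent choice for not missing late events. This stands as a reason to keep the planned tables. It does not explain the absence of an on-treatment view, since only persistence for the full 42 days removes the dilution.

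Other outputs are already tied to dosing days. ECG and blood pressure are summarised by day and time point, i-STAT likewise on Days 1 and 14, and heart rate and QTcF are modelled by time point. This stands too, and limits the point to symptomatic events. The causality table is more specific to drug effect, but it rests on investigator judgement and is not restricted by onset.

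The SAP presents counts and percentages, not rate ratios, in an exploratory study. That is right, and the expected excess in event counts survives. What is lost is precision and the visible contrast between percentages.

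Several stronger readings are tempting and not supported:

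- **That the plan blames study drug for wash-out events.** The rule allocates events to a treatment group, placebo included; causality is assessed separately.
- **That all off-drug time is spent on ipratropium.** This is stated for the wash-outs between periods. After Period 3 the schedule of assessments only shows dispensing at Visit 11, and patients who discontinue permanently receive local standard of care (Protocol 7.1.3).
- **That the window always exceeds 42 off-drug days.** This depends on what last dose means, which the SAP leaves open.
- **That a tolerability difference will be masked.** The dilution is conditional on how long the excess lasts.

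**Conclusion.** The point holds as a gap in presentation, not an error in the planned tables. About 75% of each treatment's TEAE window is off study drug, and no planned table isolates onset during dosing. For symptomatic events a true on-drug rate ratio of 2 would appear as anything from 1.25 to 2.0, depending on whether the excess stops at the last dose or lasts the full 42 days. In the first case the z-score is about 58% of its on-treatment value.

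These figures assume a constant background rate, Poisson counts and no allowance for pairing. The half-lives are not given, so no single value in the range can be preferred. The documents do not support a reading that the safety comparison is invalid: allocation is symmetric and the expected excess in event counts is preserved.

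**What to change.** Keep the 42-day TEAE tables as planned. Add to SAP 4.4.1.1 one table by SOC, PT and treatment for onset from the first dose to 24 h after the last dose taken in each period, with wash-out onset in a separate column so that no event is lost. State that a patient with the same term in both intervals counts once in each column.

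In SAP 3.5.1, state whether the 42-day limit runs from the last dose of each period or of the study. On the second reading, days 43 to 49 of the first two wash-outs also count.

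No new data are needed: AE start date and time are collected (Protocol 8.3.4), and the 24 h split already exists in SAP 3.2.3. The cost is one table with smaller cell counts. Some late drug-related events may fall in the wash-out column: Protocol 2.3 reports bronchodilation up to 36 hours after single doses. The two columns should therefore be read together.
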